5.3 Subject Withdrawal Criteria

5.3.1 Screen Failures

Screening evaluations will be used to determine the eligibility of each subject for enrollment. Subjects who fail to meet eligibility criteria during screening evaluations will be considered screen failures and will not participate in the study. However, subjects who fail the first screening evaluation are allowed to be re-screened once.

5.3.2 Removal of Subjects

Subjects may voluntarily withdraw from the study, or be removed from the study at the discretion of an Investigator or Sponsor at any time. An Investigator may withdraw a subject at any time if it is determined that continuing the study would result in a significant safety risk to the subject.

If such withdrawal occurs, or if the subject fails to return for visits, an Investigator should determine the primary reason for a subject's premature withdrawal from the study and record the reason in the respective subject's study documents.

Subjects may withdraw or be withdrawn from the study for the following reasons:

1. At their own request or at the request of their legally acceptable representative

2. If, in an Investigator's opinion, continuation in the study would be detrimental to the subject's well-being
3. At the specific request of the sponsor

Also subjects may be withdrawn for the following reasons:

- Noncompliance with the protocol requirements
- Difficulties with blood collection
- Pregnancy
- AE
- Unanticipated event that could result in an inadequately characterized PK profile (such as missed PK blood samples, for example)
- Other

In all cases, the reason for withdrawal must be recorded in the eCRF and in the subject's records.

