5.3.3 Subject Replacement

Subjects who are withdrawn from the study will not be replaced.

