5.3.4 Follow-up of Subjects Withdrawn from Study

Subjects who receive any amount of IP and discontinue early from the study will be requested to return for the early discontinuation visit procedures within approximately 7 days following discontinuation.

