- Vital signs measurement (HR, BP, RR, and body temperature) prior to study drug injection, 60 minutes post study drug injection (a window of ± 10 minutes is permitted) and 12 hours post study drug injection (a window of ± 10 minutes is permitted)
- Record AEs and concomitant medications prior to and post study drug injection
- Study drug injection

- PK blood sampling prior to study drug injection, 60 minutes post study drug injection (a window of ± 10 minutes is permitted) and 12 hours post study drug injection (a window of ± 1 hour is permitted)
- Injection site evaluation 60 minutes (± 10 minutes) post study drug injection (Note: any reactions will be recorded as AEs)

Day 2:

- Record concomitant medications
- Record AEs
- PK blood sample will be collected approximately 24 hours following study treatment administration (a window of ± 1 hour is permitted)
- Injection site evaluation approximately 24 hours post study drug injection (prior to discharge) (Note: any reactions will be recorded as AEs)
- Symptom-directed physical examination approximately 24 hours post study drug injection (prior to discharge)
- Subjects will be discharged from the clinical research unit on Day 2, following clinical assessments and procedures, and will return for each of the remaining scheduled ambulatory visits (from Days 3 to 150).

Day 3 to Day 115:

A PK blood sample will be collected on each of the following days:

- Days 3, 4 and 5 (a window of ± 4 hours is permitted)
- Days 7, 10, and 14 (a window of ± 1 day is permitted)
- Days 21 and 28 (a window of ± 2 days is permitted)
- Days 60, 79, and 115 (a window of ± 4 days is permitted)

Procedures performed on Days 3, 4, 5, 7, 10, 14, 21, 28, 60, 79 and 115 (the window for these procedures is the same as that for the PK sample to be collected on the same study Day):

- Record concomitant medications
- Record AEs
- Vital signs measurement (HR, BP, RR, and body temperature) (Day 5, 28, and 60 visits only)
- Symptom-directed physical examination (Day 5, 28, and 60 visits only)
- Clinical laboratory assessments (chemistry, hematology, urinalysis) (Day 5, 28, and 60 visits only) (see [Table 7-1](#) for details)

Final Visit (Day 150 ± 7 days)/Early Discontinuation Visit:

- Record concomitant medications
- Record AEs

- A PK blood sample will be collected
- Full physical examination (excluding breast and genitourinary examination)
- Vital signs measurement (HR, BP, RR, and body temperature)

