8.4 Type and Duration of the Follow-Up of Subjects after Adverse Events

In so far as is possible, all individuals will be followed up until the AE or suspected ADR has been resolved. If an AE/suspected ADR/SAE is present when the subject has completed the study, the course of the event must be followed until the final outcome is known, or the event has been stabilized and no further change is expected and an Investigator decides that no further follow-up is necessary.

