9.1.2 Efficacy Analysis

The percentage of subjects maintaining anti-HAV antibody levels ≥ 10 mIU/mL up to Day 60 following study treatment administration will be listed and summarized. The anti-HAV antibody levels during the PK sampling period (up to Day 150 following study treatment administration) will be listed and summarized. N, mean (SD), 90% CI for mean, % coefficient of variation (CV), median, minimum, maximum, geometric mean will be provided. The individual plasma and/or serum concentration/time profiles will be presented using the actual sampling times whereas the mean plasma and/or serum concentration/time profiles will be presented using the nominal sampling times.

The efficacy analyses will be performed on the evaluable and safety populations (if different).

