9.3 Level of Significance to Be Used

Not applicable since only descriptive statistics will be provided and there will be no statistical hypothesis testing.

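### Section 5.3.2 lets a subject be withdrawn from the whole study because missed PK samples could spoil the PK profile; used before about Day 49, this gives up an otherwise obtainable Day 60 titer.

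*Protocol*

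**What the plan says.** Section 5.3.2 separates two lists of reasons for leaving the study. The second, introduced as reasons for which subjects may be withdrawn, includes "Unanticipated event that could result in an inadequately characterized PK profile (such as missed PK blood samples, for example". The withdrawal is from the study as a whole; with a single injection on Day 1 there is no further treatment to stop.

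The consequences are set elsewhere in the protocol:

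- Section 5.3.3: "Subjects who are withdrawn from the study will not be replaced".
- Section 5.3.4: subjects who received any IP and leave early "will be requested to return for the early discontinuation visit procedures within approximately 7 days following discontinuation".
- Section 7.3.1, on the late sampling visits: "Days 60, 79, and 115 (a window of ± 4 days is permitted". For the final or early discontinuation visit it states "A PK blood sample will be collected", together with a full physical examination, vital signs, laboratory tests, retain samples, and AE and concomitant medication recording.
- Section 7.1.1: the primary variable is the proportion of subjects who keep a titer of at least 10 mIU/mL up to 60 days.
- Section 9.1.4 analyses PK at actual sampling times and sets concentrations that cannot be determined to missing. Section 9.7.3 lets a subject with an incomplete sampling schedule contribute the PK parameters that the gap does not affect.

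**The concern.** The bullet lets a problem with the PK profile end a subject's contribution to the primary endpoint. A subject who misses, say, two early samples may have a poorly described absorption phase and yet be able and willing to attend on Day 60. That visit is the only scheduled sample between Day 28 and Day 79, and it decides whether protection lasted as long as the primary objective asks. Withdrawal removes that visit, and nothing in section 5.3 keeps the subject on it.

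The exchange brings no analytic gain. The PK analysis does not need the withdrawal, because 9.1.4 and 9.7.3 already cover missing and incomplete data. The efficacy analysis does not need it either: 9.7.2 excludes only subjects without the full dose or with major deviations affecting efficacy up to Day 60. In a study of about 28 subjects without replacement, an avoidable loss should not be written in as a listed option. The scheduled safety visits after the early discontinuation visit are given up as well.

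**Working it through.** **The plan's own figure.** Section 9.2 expects about 20 evaluable from about 28 enrolled at about 30% dropout: 28 × (1 − 0.30) = 19.6, about 20. This reproduces. One lost subject is 1/28 = 3.6% of those enrolled.

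**When the Day 60 value is lost.** Inputs: Day 60 with ±4 days (7.3.1, Table 7-2); an early discontinuation visit within about 7 days (5.3.4).

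- Day 60 window: 60 − 4 = Day 56 to 60 + 4 = Day 64.
- Earliest discontinuation from which the visit can reach the window: 56 − 7 = Day 49.
- Discontinuation on Day 48: visit by 48 + 7 = Day 55, one day short.
- Discontinuation on Day 30 (latest Day 28 visit, 28 + 2): visit by Day 37, 19 days short.
- The 7 days is approximate. Assuming 5 days, the cut-off is 56 − 5 = Day 51; assuming 10 days, it is 56 − 10 = Day 46.
- From about Day 49 until the Day 60 sample an in-window value is possible but not assured, since the visit may take place sooner than the limit.

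**PK samples forgone (Table 7-2, 16 samples).**

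| Discontinuation just after | Samples forgone | Number |
|---|---|---|
| Day 28 sample | 13 to 16 | 4 |
| Day 10 sample | 10 to 16 | 7 |
| Day 5 sample | 08 to 16 | 9 |

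For discontinuation before Day 49 the loss is therefore at least 4, and exactly 4 only once the Day 28 sample has been taken. One early discontinuation sample is gained in return.

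**Safety assessments forgone, for withdrawal between Day 28 and about Day 48.** After Day 28, examination, vital signs and laboratory tests are scheduled only at Days 60 and 150. The early discontinuation visit has the same content as the Day 150 visit and stands in for it. The net loss is one examination and laboratory occasion (Day 60), an earlier last assessment, and AE enquiry at the later visits. In calendar time, with the visit by Day 55, scheduled AE collection ends 150 − 55 = 95 days early, or 95/150 = 63% of the period. That is elapsed time, not a share of the assessments.

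**Effect on the primary result (illustration).** Assume 20 evaluable subjects, all protected. The exact 95% lower bound is 83.2% for 20/20. If one is lost and left out, it is 82.4% for 19/19. If the lost subject is counted as a failure, the result is 19/20 = 95% with a lower bound of 75.1%. Which of these applies depends on missing-data handling, which section 9.5 leaves to the SAP.

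**The case against.** The strongest reply is that nothing here is an error. The rule says only that subjects may be withdrawn, the 30% dropout allowance already covers losses, and under section 9.3 "only descriptive statistics will be provided and there will be no statistical hypothesis testing", so no conclusion turns on one subject. Other text leans towards keeping data: 7.3.2 calls for recollecting samples that cannot be analysed, and 9.1.4 accepts samples outside their windows. All of this stands and limits the size of the point. None of it keeps a subject withdrawn under this bullet on the Day 60 visit, and none of it gives the bullet a benefit. An SAP can say how to treat a missing titer but cannot recover a sample that was never drawn.

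A second reply is that noncompliance, the catch-all reason, or the general discretion of investigator and sponsor could remove the same subject, so deleting one bullet would change little. That is right, and the fix has to cover those routes.

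Three stronger readings are tempting, and the documents do not support them:

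- A reader might infer that 5.3.2 contradicts 9.7.3. It does not. One permits withdrawal; the other says how incomplete profiles are analysed. Both can be followed.
- A reader might infer that missed samples oblige the site to withdraw the subject. The wording is permissive.
- A reader might infer that safety follow-up is abandoned. The early discontinuation visit is a full assessment, and for events already present section 8.4 states: "In so far as is possible, all individuals will be followed up until the AE or suspected ADR has been resolved". What is lost is the later scheduled visits and the detection of new events at them.

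**Conclusion.** The point holds as a minor design weakness. If this ground is used before about Day 49 (Day 46 to 51 under assumed allowances of 10 to 5 days), a Day 60 value that a willing subject could still give is lost, together with at least 4 scheduled PK samples and, after Day 28, one net examination and laboratory occasion and later AE enquiry. Each case is 3.6% of the planned enrolment. How often the ground would be used cannot be derived from the protocol.

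The conclusion assumes that the subject would have attended Day 60. Withdrawal after the Day 60 sample costs no primary data. A subject whose titer had already fallen below 10 mIU/mL at an earlier sample has a known outcome. A retained subject might still be left out of the evaluable population under 9.7.2, but the Day 60 value would count in the safety population, since section 9.1.2 says: "The efficacy analyses will be performed on the evaluable and safety populations (if different".

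**What to change.** In 5.3.2, replace the bullet with a sentence such as:

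*An incomplete PK profile, including missed PK samples, is not by itself a reason to withdraw a subject from the study under any ground in this section, including Noncompliance or Other; willing subjects continue the remaining scheduled visits, including Day 60 and Day 150, and incomplete profiles are handled under 9.7.3.*

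Leave withdrawal for subject request, safety, AE, pregnancy and difficulties with blood collection as it is. Naming the noncompliance and catch-all grounds matters, because otherwise the same subject could be removed by another route and the retained text would pull against the new sentence.

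The cost is one bullet replaced, slightly more site work on visits that are already planned, and some incomplete PK profiles to handle in the analysis.

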5.3.3 Subject Replacement

Subjects who are withdrawn from the study will not be replaced.

5.3.4 Follow-up of Subjects Withdrawn from Study

Subjects who receive any amount of IP and discontinue early from the study will be requested to return for the early discontinuation visit procedures within approximately 7 days following discontinuation.

6 TREATMENT OF SUBJECTS

See Section 4.4 for the treatment to be administered, including the name of the IP, the dose, the dosing schedule and the route/mode of administration.

6.1 Administration and Timing of Investigational Products for Each Subject

Administration of the IP will be staggered between subjects for the purpose of accurate sampling time.

A single 0.2 mL/kg dose of the IP will be injected intramuscularly in the anterolateral aspects of the upper thigh or the deltoid muscle of the upper arm.

Doses over 5 mL are to be divided and injected into several muscle sites to reduce local pain and discomfort.

The gluteal region should not be used as an injection site due to the risk of injury to the sciatic nerve. The IP is not to be administered subcutaneously or intravenously.

The subjects will be discharged from the clinic on Day 2, following the scheduled assessments and clinical procedures. Subjects will be asked to return to the clinic for the remaining PK blood samples and clinical assessments, and for the final visit.

6.2 Prior and Concomitant Therapy

Concomitant medications must be recorded in the eCRF, including the trade and generic names of the medication, the dose, the route of administration, and the duration of the medication (frequency).

6.2.1 Prohibited Medications Prior to Study Participation

As per the exclusion criteria (see section 5.2), subjects are prohibited from taking any of the following prior to study participation:

1. Any type of IG, including HAV IG
2. Estrogens (for at least 30 days prior to the study drug administration and during the entire study duration)
3. Any plasma-derived product infusion
4. Any blood or plasma transfusion
5. Any live virus vaccine
6. Any anti-viral treatment, regardless of the route of administration
7. Any dose of parenteral, oral, or inhaled corticosteroids, immunosuppressants, or immunomodulators

6.2.2 Prohibited Concomitant Medications during the Study

In addition to the medications listed in section 6.2.1, subjects are prohibited from taking any IPs that are not for this study.

6.2.3 Restricted Concomitant Medications during the Study

No concomitant medications will be restricted during the study with the exception of any medication described in section 6.2.1.

6.3 Treatment Compliance

Reasons for any deviation from the administration of less than 100% of the IP dose, as prepared by the pharmacist or designee, must be recorded in the eCRF and in the subject's medical records.

To ensure treatment compliance, study treatment administrations will be observed and verified by a site staff member.

7 ASSESSMENT OF EFFICACY AND PHARMACOKINETICS

7.1 Efficacy Variables

7.1.1 Primary Efficacy Variable

The primary efficacy variable in this study is the proportion of subjects maintaining protective anti-HAV antibody levels (defined as anti-HAV antibody titer ≥ 10 mIU/mL in plasma and/or serum) up to 60 days after study treatment administration.

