2.4.2 Justification for Selection of Doses/Timing of Investigational Products

Recently the Food and Drug Administration (FDA) approved and instituted an anti-HAV titer specification (Not Less Than >20 IU/mL) and revised dosing for GamaSTAN S/D. Due to the recently instituted titer specifications and revised dosing, Grifols committed to the FDA to evaluate anti-HAV titers following IM administration at the recommended dose of 0.2 mL/kg in non-HAV (seronegative) healthy volunteers. An IM dose of 0.2 mL/kg was chosen, as it is the recommended dose for prophylaxis prior to exposure to hepatitis A for persons traveling to areas endemic with the virus.

Peak levels of IgG are obtained approximately 2 days after IM injection of immunoglobulins⁽¹²⁾. The half-life of IgG in the circulation of individuals with normal IgG levels is 23 days⁽⁹⁾. In this study, a 150-day follow-up period is chosen as it represents approximately 5 half-lives.

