7.3.3 Drug Concentration Measurements

Total anti-HAV antibody levels will be measured in the subjects throughout the study.

Table 7-2 PK Blood Sampling Schedule

Sample Number	Study Day	Time (Window)
01	1	Prior to treatment administration
02	1	60 minutes following treatment administration (±10 minutes)
03	1	12 hours following treatment administration (±1 hour)
04	2	24 hours following treatment administration (±1 hour)
05	3	48 hours following treatment administration (±4 hours)
06	4	72 hours following treatment administration (±4 hours)
07	5	96 hours following treatment administration (±4 hours)
08	7	(±1 day)
09	10	(±1 day)
10	14	(±1 day)
11	21	(±2 days)
12	28	(±2 days)
13	60	(±4 days)
14	79	(±4 days)
15	115	(±4 days)
16	150	(±7 days)

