9.1.4 PK Analysis

Anti-HAV antibody plasma and/or serum concentrations produced by the administration of the study treatment will be determined in order to establish the PK profile of the IP. The PK parameters that will be derived from the plasma and/or serum concentrations *versus* time profiles are listed in [Table 9-1](#). All reported sampling time deviations will be taken into consideration for evaluation of PK parameters. It is recognized that there may be circumstances where PK sampling may fall outside of the time windows. The actual times for collection of PK samples will be captured in the source data and eCRF for analysis.

In the case where concentrations of anti-HAV antibodies cannot be determined due to bioanalytical or clinical reasons, these values will be set to missing for the statistical and PK analyses.

The main PK parameters of interest for this study will be $AUC_{0-\infty}$, AUC_{0-T} , C_{max} , T_{max} , λ_z , T_{half} , Cl_{TOT}/F and V_D/F .

Table 9-1 Pharmacokinetic Parameters

PK Parameter	Definition
C_{max}	Maximum observed plasma and/or serum concentration
T_{max}	Time of maximum observed plasma and/or serum concentration; if it occurs at more than one time point, T_{max} is defined as the first time point with this value
T_{LQC}	Time of last observed quantifiable plasma and/or serum concentration
AUC_{0-T}	Cumulative area under the plasma and/or serum concentration time curve calculated from 0 to T_{LQC} using the linear trapezoidal method, where T_{LQC} represents time of last observed quantifiable plasma and/or serum concentration
$AUC_{0-\infty}$	Area under the plasma and/or serum concentration time curve extrapolated to infinity, calculated as $AUC_T + C_{LQC}/\lambda_z$, where C_{LQC} is the measured concentration at time T_{LQC}
T_{LIN}	Time point where the log-linear elimination phase begins
λ_z	Apparent elimination rate constant, estimated by linear regression of the terminal linear portion of the log concentration versus time curve
T_{half}	Terminal elimination half-life, calculated as $\ln(2)/\lambda_z$
V_D/F	Apparent Volume of Distribution, calculated as follows: $V_D / F = \left(\frac{Dose}{K_{el} * AUC_{\infty}} \right)$
Cl_{TOT}/F	Apparent Total plasma and/or serum Clearance, calculated as follows: $Cl_{TOT} / F = \left(\frac{Dose}{AUC_{\infty}} \right)$

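### Is the primary endpoint read 60 days after dosing or at the Day 60 visit, and does the difference matter?

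*Protocol*

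**What the plan says.** The Synopsis, section 4.1 and section 7.1.1 define the primary efficacy variable in elapsed time: the proportion of subjects whose titer stays at or above 10 mIU/mL "up to 60 days after study treatment administration". The objective in section 3.1 also speaks of 60 days. Section 9.1.2, and the Synopsis paragraph on efficacy analysis, use a study-day label: the percentage maintaining that level "up to Day 60 following study treatment administration will be listed and summarized". The evaluable population in section 9.7.2 also runs to Day 60.

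The injection is given on Day 1. Table 7-2 in section 7.3.3 ties study days to post-dose time early on: the Day 2 row reads "24 hours following treatment administration (±1 hour") and the Day 5 row "96 hours following treatment administration (±4 hours"). For the Day 60 sample (number 13) it prints only the window of ±4 days, as does section 7.3.1 under "Days 60, 79, and 115 (a window of" ±4 days). Nothing is scheduled between Day 28 and Day 60.

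Three other statements bear on the point:
- Section 2.4.2: "The half-life of IgG in the circulation of individuals with normal IgG levels is 23 days".
- Section 9.1.4: "The actual times for collection of PK samples will be captured in the source data and eCRF for analysis".
- Section 9.3: the statistics are descriptive only, with no hypothesis test.

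**The concern.** A responder endpoint with a fixed cut-off, read on a falling concentration curve, depends on when blood is drawn. If the definition means 60 elapsed days and the analysis means study Day 60, they refer to different times, and the offset favors the product because an earlier sample reads higher. One draw carries most of the weight: for a subject above the threshold at Day 28, the Day 60 sample settles the outcome. The ±4-day window widens the issue, since a sample taken 55 days after dosing cannot by itself show protection to 60 days. This is the only efficacy endpoint, in a study that section 2.4.2 ties to a commitment to the regulator on anti-HAV titers. A reported proportion that did not match the stated objective would be a fair criticism.

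**Working it through.** **1. Day count.** With dosing on Day 1, post-dose time = (study day − 1) × 24 h. Days 2, 3, 4 and 5 give 24, 48, 72 and 96 h, exactly as printed in Table 7-2. The same rule puts Day 60 at 59 days and its window (Day 56 to Day 64) at 55 to 63 days. Table 7-2 prints no hours for Day 60, so 59 days is an inference from the convention.

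**2. Size of the one-day difference.** With half-life T, the ratio of the titer at 60 days to that at 59 days is 2^(−1/T).
- T = 23 days (section 2.4.2): 2^(−1/23) = 0.970, a fall of 3.0%.
- T = 30 days (from the protocol's 150 days as approximately 5 half-lives, 150/5): 2^(−1/30) = 0.977, a fall of 2.3%.

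At T = 23, a subject drawn at exactly 59 days is classed differently only if the 60-day titer lies between 10 × 0.970 = 9.7 and 10 mIU/mL.

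**3. Size of the window.** At T = 23, relative to the 60-day level, a sample reads 2^(5/23) = 1.163 at 55 days and 2^(−3/23) = 0.914 at 63 days. A measured 10.0 then corresponds to 8.6 or 10.9 mIU/mL at 60 days. Over the 8 days the titer falls by 1 − 2^(−8/23) = 21%. This is larger than the one-day offset, but it comes from the openly stated visit window and would remain under either wording.

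**4. Effect on the proportion.** The protocol gives no expected titer at 60 days, so these inputs are assumptions: lognormal titers, CV 30%, geometric mean (GM) 12, 15 or 20 mIU/mL, no assay error, T = 23.

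P(t) = Φ{[ln(GM/10) + ln 2 × (60 − t)/T]/s}, with s = √ln(1 + 0.3²) = 0.2936.

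For GM 12:
- At 60 days: Φ(0.1823/0.2936) = 73.27%.
- At 59 days: Φ((0.1823 + 0.0301)/0.2936) = 76.54%.

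The standard error is √[p(1 − p)/20], with p taken at 60 days. Differences are from unrounded values.

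| GM | True at 60 d (%) | All drawn at 59 d (%) | Difference (points) | Draws even over 55–63 d (%) | Difference (points) | SE, n = 20 (points) |
|---|---|---|---|---|---|---|
| 12 | 73.27 | 76.54 | +3.27 | 75.93 | +2.65 | 9.90 |
| 15 | 91.64 | 93.11 | +1.47 | 92.56 | +0.92 | 6.19 |
| 20 | 99.09 | 99.31 | +0.22 | 99.18 | +0.09 | 2.12 |

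In subjects out of 20, the shift is 0.65, 0.29 and 0.04 when all draws are at 59 days, and 0.53, 0.18 and 0.02 when draws spread evenly over the window. It is at most about a third of the standard error (3.27/9.90 = 0.33).

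**5. The wordings side by side.** The phrase in section 9.1.2 does not stop at Day 60. It goes on to count from treatment administration, so it can be read as 60 days after dosing. The protocol also treats a day label and a number of days as the same thing elsewhere: sections 2.4.2 and 4.5 call follow-up to the Day 150 visit a period of 150 days. On either reading, sample 13 is the only scheduled sample that can serve the endpoint, so at nominal timing no subject is classified differently.

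**The case for a change.** The best argument for a change is that the two readings can part company inside the window. Take a draw at 62 days reading 9.8 mIU/mL. By visit, the subject fails. On strict elapsed time the draw lies past the 60-day limit, and the back-projected level is 9.8 × 2^(2/23) = 10.4, a success. The wording is cheap to harmonize, and a sensitivity analysis interpolated to exactly 60 days needs no new samples.

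Part of this stands. The wording is loose, the offset favors the product, and an in-window draw can fall on either side of 60 days. Three things weaken it as a reason to change the plan.

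- Applying the elapsed limit strictly would discard a valid in-window Day 60 sample and leave Day 28 as the last reading. An analyst would not do that; the natural course is to take the Day 60 visit as scheduled.
- Harmonized wording would leave the window effect where it is. How in-window samples count is ordinary SAP content, and sections 9.1 and 9.5 send data handling there.
- Interpolation gains little. In simulation (GM 15, CV 30%, half-life 23 days), misclassification against the true 60-day status fell from 3.5% to 1.9% at an assay CV of 5%, and from 4.8% to 3.9% at 10%. That is 0.3 and 0.2 of 20 subjects (0.016 × 20 and 0.009 × 20), and it brings in the assay error of a second sample.

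**Conclusion.** The inconsistency is real but clerical, and the plan can stand. Followed as written, it gives a sound descriptive proportion at the Day 60 visit, nominally 59 days after dosing. The wording difference is worth one day, or 2.3% to 3.0% of the titer at half-lives of 30 to 23 days. In the settings tabulated it shifts the proportion by 0.2 to 3.3 points if every sample is drawn at 59 days, well inside sampling error for 20 subjects. No test or success threshold turns on it. Titers are listed, actual draw times are captured and individual profiles are plotted on actual times, so a reader can see when each subject was measured.

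The proportions rest on assumed lognormal titers with CV 30% and geometric means of 12 to 20 mIU/mL. The closer typical titers lie to 10 mIU/mL, the larger the shift. A formal pass mark for the proportion would also make the timing rule matter more, but this protocol sets none.
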